Encouraging Blood Donation in Patients With a Blood Type in Short Supply – Part 2

Protocol and Statistical Analysis Plan

NCT05825300

July 3, 2023

Protocol

Scientific background

There has been a years-long national shortage of several blood types in the U.S., including in the Geisinger community. Previously, the study team collaborated with Miller Keystone, where Geisinger refers patients who wish to donate blood and from whom Geisinger receives blood for clinical purposes, on an outreach study to encourage blood donation in patients with needed blood types. The study demonstrated that, compared with a no-message control group, patient portal messages sent to patients with needed blood types increase patients' likelihood of attending donation appointments. However, results were ambiguous with respect to which of two message versions was most effective. One version, which stated that the patient had a needed blood type (blood-type message), caused a numerically, but not significantly, higher number of patients who attended appointments compared to the other version, which did not state that the patient had a blood type in need but rather informed the recipient of a general blood shortage (no-blood-type message).

Because Miller Keystone particularly values reaching new donors, the team ran a preregistered exploratory analysis to test whether the messages were differently effective for new donors compared to those who had previously donated at a Miller Keystone site. There was a significant interaction between previous donor status (previous donor, previous non-donor) and message type, such that previous non-donors were relatively more responsive to the blood-type message, while previous donors were more responsive to the no-blood-type message. However, the groups were uneven with respect to the number of patients that had previously donated. Moreover, when the analysis was limited to patients who opened their messages, this interaction effect disappeared: blood-type messages were still most effective in previous non-donors, and there was no difference in message effectiveness among previous donors. These follow-up analyses, and the unevenness of previous donors across groups, call into question the robustness of the interaction effect.

Objectives

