The present study again tested whether the blood-type message is more effective than the no-blood-type message for patients with needed blood types overall, and separately for previous donors and non-donors. Messages in the present study were sent via email rather than via patient portal. Randomization occurred at the email-address level to one of the two message types to ensure everyone using the same email address received the same message (although each patient was sent an individualized message with their name; there was no no-contact control condition this time). Email addresses were excluded if they were shared by patients with different blood types. Randomization was stratified by whether all patients using the same email address are previous donors or not (email addresses shared by previous donors and non-donors were excluded).

Design

This study is a randomized controlled trial with 2 study arms.

Methods

Email addresses of patients enrolled in the study were randomized to the following arms:

1. No-blood-type message – a message that did not mention the patient had a needed blood type
2. Blood-type message – a message that mentioned the patient had a needed blood type

Randomization was stratified by previous donor status of all patients at an email address.

Power analysis

Our sample includes 40,486 patients with a total of 40,130 email addresses. 39,317 email addresses are associated with patients who are previous non-donors, and 813 email addresses are associated with patients who are previous donors.

Within the previous non-donor group, we will have 80% power to detect an increase in the primary outcome from 0.07% (the primary-outcome rate in previous non-donors who were sent a no-blood-type message in our previous study) to 0.16%, with a two-tailed alpha of .05.

Within the previous donor group, we will have 80% power to detect an increase in the primary outcome from 4.76% (the primary-outcome rate in previous donors who were sent a no-blood-type message in our previous study) to 9.87%, with a two-tailed alpha of .05.

Note that a portion of the sample will be excluded from analysis (e.g., those whose emails were not sent or bounced; see the *Analysis notes* section for details).

Project status

All emails have been sent. No outcome data have been extracted.

Statistical Analysis Plan

Primary outcome

Number of Participants Who Attended a Donation Appointment

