Timeframes listed refer to the amount of time elapsed from the send date for a given patient. For instance, the primary outcome timeframe is 6 weeks; thus, for the purposes of this study, a

patient will be counted as having donated if they donated blood within 6 weeks of their message send date.

As a robustness check, we will rerun the analyses above on the subset of patients who open the messages, using a time frame of 6 weeks from the date each individual patient opened their message (rather than 6 weeks from the patient's message send date).

We will run an additional robustness check including only patients who scheduled an appointment within the 2 weeks following their message send date.

Recent work suggests that OLS regressions are appropriate in randomized experiments with binary outcome variables such as ours (Gomila, 2021).

Other prespecified outcomes

We will use the approaches described in *Analyses 1* and *2* above to evaluate the impact of the intervention on the other prespecified outcome measures listed in the pre-registration:

1. Number of Participants Who Successfully Donated Blood

Attended a donation appointment within 6 weeks of their message send date and successfully donated, excluding patients who were turned away from or left their appointment without donating.

[Time Frame: Within 6 weeks of the patient's message send date]

2. Number of Participants Who Scheduled a Blood Donation Appointment

Scheduled an appointment within 2 weeks of their message send date.

[Time Frame: Within 2 weeks of the patient's message send date]

3. Number of Participants Who Scheduled a Blood Donation Appointment

Scheduled an appointment within 6 weeks of their message send date.

[Time Frame: Within 6 weeks of the patient's message send date]

Additional exploratory analyses

1. Primary outcome in the full sample

We will run an OLS regression to test whether the primary outcome varies as a function of experimental group in the full sample, without dividing the sample by previous donor status.

2. New donors vs. previous donors

We will run an OLS regression to test whether the primary outcome varies as a function of experimental group, a bivariate indicator for whether or not the patient previously donated blood, and the interaction between these variables.

3. Time to donation

We will run regression models to test whether either intervention message influenced the timing (time elapsed since the message was sent) of donations.

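### Exploratory analysis 2 names no standard-error type for its OLS interaction test; with the ordinary one, the test rejects a true null about 69% of the time at the plan's own rates

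*Combined protocol and SAP*

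**What the plan says.** Under Additional exploratory analyses, item 2 (New donors vs. previous donors), the SAP plans a single OLS regression across both strata. The predictors are message group, "a bivariate indicator for whether or not the patient previously donated blood, and the interaction between these variables". The Analysis notes set the email address as the unit of analysis. They support OLS for a binary outcome with one sentence citing a methods paper. No section says whether standard errors are ordinary, robust or of another kind.

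The Scientific background explains the interest in this contrast. Of the earlier study it says: "There was a significant interaction between previous donor status (previous donor, previous non-donor) and message type". It then says that follow-up analyses and uneven groups "call into question the robustness of the interaction effect".

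The Power analysis section gives the stratum sizes: "39,317 email addresses are associated with patients who are previous non-donors, and 813 email addresses are associated with patients who are previous donors". It gives the planning rates as "0.07% (the primary-outcome rate in previous non-donors who were sent a no-blood-type message in our previous study") and "4.76% (the primary-outcome rate in previous donors who were sent a no-blood-type message in our previous study"). It also warns: "Note that a portion of the sample will be excluded from analysis". The fraction to be excluded and the allocation ratio are not stated.

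**The concern.** The ordinary OLS standard error uses one residual variance, estimated over all addresses. That is harmless when the compared groups have similar variances, or when each contrast draws on the strata in proportion to their size. The interaction does neither. It subtracts the message effect in non-donors from the message effect in donors, and nearly all of its uncertainty comes from the 813 donor addresses. Those addresses are 2% of the sample and have by far the larger outcome variance. A pooled variance diluted by 39,317 near-zero-variance addresses is far too small for the donor contrast. Donor status is not randomized, so balanced message arms give no protection.

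At stake is the only planned direct test of whether the message effect differs by donor status. Analyses 1 and 2 estimate the effect within each stratum but do not test the difference. With ordinary standard errors, exploratory analysis 2 could appear to confirm the earlier interaction, which the plan itself doubts, when none exists.

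**Working it through.** **Inputs.** From the Power analysis section: 813 donor addresses at 4.76% and 39,317 non-donor addresses at 0.07%. Assumed: 1:1 allocation in each stratum, a two-sided 5% level, no message effect in either stratum, no exclusions at first.

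**The plan's own figures.** For donors, 4.76% against 9.87% with 406.5 addresses per arm (two-proportion test, pooled variance) gives z = (0.0511·√406.5 − 1.96·√0.1356)/√0.1343 = 0.842, so power is 80.0%, as stated. For non-donors, the printed 0.07% and 0.16% give 74.9%. Reading 0.07% as a rounded 0.065% gives 80.2%, so rounding can explain that gap.

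**Outcome variances, p(1 − p).**
- Donors: 0.0476 × 0.9524 = 0.0453
- Non-donors: 0.0007 × 0.9993 = 0.0007
- Ratio: about 65

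**Pooled residual variance.** (813 × 0.0453 + 39,317 × 0.0007)/40,126 = 0.00160, about 28 times smaller than the donor variance.

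**Standard error of the interaction.**
- Ordinary: √[0.00160 × (4/813 + 4/39,317)] = 0.00284
- True: √[0.0453 × 4/813 + 0.0007 × 4/39,317] = 0.01494
- Ratio, ordinary to true: 0.19

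**Type I error.** The normal approximation gives 2Φ(−1.96 × 0.19) = 71%. In 500,000 simulated null trials, rejection was 69.0% with the ordinary standard error and 5.0% with either HC2 or HC3. The mean ordinary standard error was 0.0028 and the true SD 0.0150. A separate run of 400,000 trials also gave 69.0% (ordinary), with HC1, HC2 and HC3 at 5.0–5.1%. Full regression fits to 600 simulated data sets gave 70.2% (ordinary) and 5.8% (HC2), within Monte Carlo error.

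**In counts.** About 406.5 × 0.0476 = 19 attenders are expected per donor arm. If the non-donor arms are equal, the ordinary test needs a donor difference above 1.96 × 0.00284 × 406.5 = 2.3 attenders, so 3 suffice. With the true standard error the threshold is 1.96 × 0.01494 × 406.5 = 11.9, so 12 are needed.

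**Worked data set.** Take 19/406 against 22/407 donor attenders, and 14 against 14 non-donor attenders. The interaction coefficient is 0.0073.
- Ordinary SE 0.0029, p = 0.012
- HC2 SE 0.0154, p = 0.64
- Analysis 2 on the same donors: p = 0.64

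**Conflict with the stratum results.** In 61% of the simulated null trials the ordinary interaction test was significant while neither Analysis 1 nor Analysis 2 was.

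**Sensitivity of the 69%.**

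| Scenario | Type I error, ordinary SE |
|---|---|
| Donor 2%, non-donor 0.2% | 51% |
| Donor 10%, non-donor 0.05% | 77% |
| Donor rate 9.87% | 75% |
| Non-donor rate 0.16% | 66% |
| Same 0.09-point message effect in both strata | 67% |
| Proportional exclusions, 30–90% retained | 67–73% |
| 30% lost, donors only | 76% |
| 30% lost, non-donors only | 68% |
| 2:1 or 1:2 allocation | 70% |

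**Other analyses with ordinary standard errors.** Type I error is 5.3% for Analysis 1, 5.0% for Analysis 2 and 4.7% for exploratory analysis 1. Within the interaction model, the non-donor message coefficient is too conservative: power for 0.07% against 0.16% is 51%, against 76% with robust standard errors. Analysis 1 already tests that effect validly.

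**The case against.** The strongest reply is that the plan never chooses the ordinary standard error. OLS names an estimator, and robust standard errors are often used with it; on that reading the test is sound and only a detail is missing. The cited methods paper might imply a variance estimator, but that cannot be checked from the documents. This part stands: 69% describes one permitted reading, not a property the plan has committed to. It does not remove the point, because the text leaves open a choice that moves type I error from 5% to 69%.

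Second, the analysis is exploratory, the interaction is not listed under Objectives, and no significance level is set for it. All true, and no primary conclusion depends on it. The 5% level is borrowed from the within-stratum power statements. But the background gives this contrast its importance, and an exploratory p-value still needs a correct standard error.

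Third, a reader could notice that Analyses 1 and 2 disagree with the interaction result. That helps only partly: a significant interaction with neither stratum effect significant is a legitimate pattern and would not by itself reveal the error.

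Fourth, the planning rates come from a patient-portal study, while this one used email. Actual rates may differ, but the ordinary standard error failed badly at every combination tried.

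**Conclusion.** The concern holds. No standard-error type is named, and with the ordinary one the interaction's standard error is about five times too small. Type I error is then about 69% at the planning rates, and 51–77% over the scenarios tried, against 5% with robust standard errors. The main figure assumes 1:1 allocation, a two-sided 5% level, no message effect in either stratum and no exclusions. It applies only if the ordinary standard error is used. The fault is confined to exploratory analysis 2, and no claim is made here about the demographic interaction models. It should be fixed, but it does not threaten the two primary questions.

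**What to change.** Add one sentence to item 2 of the Additional exploratory analyses stating that heteroskedasticity-robust standard errors (HC2 or HC3) will be used. Equivalently, test the Analysis 2 estimate minus the Analysis 1 estimate with separately estimated variances; estimating them in each of the four message-by-donor-status cells reproduces HC2. OLS and the model terms can stay as they are.

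The cost is that sentence and one option in the code. Project status says "No outcome data have been extracted", so at the document's date (July 3, 2023) the choice could still be made before results were seen. If data have been extracted since, the report should say when the standard-error type was chosen.

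### The message-by-donor-status interaction is planned only on the percentage-point scale, where at base rates of 0.07% and 4.76% it mostly repeats the donor-only comparison; a ratio-scale companion should be prespecified

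*Combined protocol and SAP*

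**What the plan says.** Under "Additional exploratory analyses", item 2, the SAP fits one OLS model with message group, "a bivariate indicator for whether or not the patient previously donated blood, and the interaction between these variables". No logistic, log-link or other ratio-scale model is named for this contrast. The Analysis notes support OLS with one sentence: "Recent work suggests that OLS regressions are appropriate in randomized experiments with binary outcome variables such as ours".

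The Scientific background says that in the earlier study "previous non-donors were relatively more responsive to the blood-type message, while previous donors were more responsive to the no-blood-type message". It adds that among patients who opened their messages the interaction went away: "blood-type messages were still most effective in previous non-donors, and there was no difference in message effectiveness among previous donors". It gives no effect sizes and does not name the model behind that result.

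The Power analysis section gives 39,317 non-donor and 813 donor email addresses. Non-donors have 80% power for "an increase in the primary outcome from 0.07"% to 0.16%; donors have 80% power for "an increase in the primary outcome from 4.76"% to 9.87%. No power is given for the interaction. Analyses 1 and 2, run separately in non-donors and donors, are the primary analyses.

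**The concern.** An OLS interaction asks whether the message adds the same number of percentage points in both groups. When one group attends at 0.07% and the other at 4.76%, two things follow.

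- **Blindness to non-donors.** An effect that more than doubles non-donor attendance is 0.09 points, far below the sampling error contributed by 813 donor addresses. The interaction then mostly restates the donor-only comparison.
- **Scale dependence.** If the message multiplies attendance by the same factor in both groups, the additive interaction is not zero and points to donors. Nothing in the plan says how such a result is to be read.

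The SAP's sentence on OLS concerns a binary outcome in a randomised comparison. Donor status is a stratification factor, not a randomised one, and the sentence does not deal with comparing effects across strata with very different base rates.

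At stake is the only planned test of whether the messages work differently in new and previous donors. The background presents that question as unsettled, and says the blood-collection partner particularly wants new donors.

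**Working it through.** **Inputs.** From the Power analysis section: 39,317 and 813 addresses; base rates 0.07% and 4.76%; detectable rates 0.16% and 9.87%; two-sided alpha .05. Assumed: 1:1 allocation within strata (the ratio is not stated), giving 19,658.5 and 406.5 addresses per arm; no exclusions (their number is not given); a robust standard error (the plan names none).

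**The plan's own figures.** Two-proportion test with pooled null variance.

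- Donors, 4.76% against 9.87%: 80.0% power, as stated.
- Non-donors, 0.07% against 0.16%: 74.9% at the printed rates. An unrounded base of 0.065% gives 80.2%, so rounding can explain the gap.

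**Base-rate ratio.** 4.76 / 0.07 = 68.0.

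**Variance of the OLS interaction.** Write a0, a1 for the non-donor rates and b0, b1 for the donor rates (0 = no-blood-type message, 1 = blood-type message).

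- Estimate: (a1 − a0) − (b1 − b0)
- Variance: [a0(1−a0) + a1(1−a1)] / 19,658.5 + [b0(1−b0) + b1(1−b1)] / 406.5

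With a0 = 0.0007, a1 = 0.0016 and b0 = b1 = 0.0476:

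- non-donor part: 0.00000012
- donor part: 2 × 0.0476 × 0.9524 / 406.5 = 0.00022305
- SE = √0.00022316 = 1.49 percentage points; donor share of the variance 99.95%

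The interaction is 0.09 points, so z = 0.09 / 1.494 = 0.06 and power is 5.0%, equal to alpha.

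**The same case on the log-odds scale.** The interaction is the difference between the two log odds ratios. Its variance is the sum over the four cells of 1 / [n p (1−p)].

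- Interaction: 0.828
- Variance: 0.0727 + 0.0318 + 0.0543 + 0.0543 = 0.2131, so SE = 0.462
- z = 1.79; power 43%

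**Other cases, same formulas.** The difference is the non-donor effect minus the donor effect; a negative sign means donors gain more points.

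| Non-donors (from 0.07%) | Donors (from 4.76%) | OLS difference, points | SE, points | OLS rejects | Log-odds rejects |
|---|---|---|---|---|---|
| 0.16% | unchanged | 0.09 | 1.49 | 5.0% | 43% |
| 0.35% (five-fold) | unchanged | 0.28 | 1.49 | 5.4% | 95% |
| 0.16% | 3.57% (down a quarter) | 1.28 | 1.40 | 15% | 65% |
| 0.16% | 2.38% (halved) | 2.47 | 1.30 | 48% | 85% |
| ratio 1.25 | ratio 1.25 | −1.17 | 1.58 | 11.5% | 5% |
| ratio 1.5 | ratio 1.5 | −2.35 | 1.66 | 29% | 5% |
| ratio 2 | ratio 2 | −4.69 | 1.80 | 74% | 5% |
| 0.16% (ratio 2.29) | 9.87% (ratio 2.07) | −5.02 | 1.82 | 79% | 5% |

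With non-donors at 0.16%, the OLS interaction reaches 80% power only if donors fall to about 1.45%.

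Simulation of the four binomial cells (200,000 draws per case) agrees. OLS rejects 5.0%, 14.8% and 48.2% of the time in rows 1, 3 and 4, and 29.3% and 74.9% at ratios 1.5 and 2. The log-odds test rejects 42.2%, 65.1% and 86.5% in rows 1, 3 and 4, and just under 5% at the two equal ratios.

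**Expected events.** The smallest planning cell is 19,658.5 × 0.0007 = 13.8. If donors halved, the donor blood-type cell would hold about 406.5 × 0.0238 = 9.7.

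**The case against.** The additive scale is a legitimate choice. The outcome is a number of attendees, and with a common ratio of 2, sending the message to every address would add about 813 × 0.0476 = 38.7 attending donor addresses against 39,317 × 0.0007 = 27.5 non-donor ones. Saying that donors gain more per email is then true. The interaction is also exploratory: Analysis 1 tells the sponsor whether the message works in non-donors, and Analysis 2 does the same for donors. All of this stands. But two separate significance results are not a test of difference, so Analyses 1 and 2 do not replace the interaction.

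A reader might infer three stronger conclusions that the documents do not support.

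- **That the test cannot detect the earlier study's pattern.** That pattern was a crossover, which is an interaction on either scale, and OLS detects it if donors fall far enough. Power is at alpha only when the effect is confined to non-donors, as in the openers analysis. With no effect sizes reported, nothing shows which case applies. Nor can one say that the scale explains why the interaction went away among openers, since the earlier model is not stated.
- **That an interaction found under equal risk ratios is a false positive.** It is real on the additive scale. How often it is declared depends on effect size, and the high figures need donor attendance to double, against the direction seen in donors before.
- **That the background's phrase "previous non-donors were relatively more responsive to the blood-type message" commits the plan to a ratio scale.** It reads as an ordinary comparison. The fault is that the scale of interpretation is left unstated.

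Two cautions on the figures also stand. The base rates come from patient-portal messages, and rates under email are unknown. The OLS results assume a robust standard error; with the classical one (about 0.28 points where the true value is about 1.49) the interaction would reject about 69–71% of the time with no message effect in either group. That is a separate defect, and curing it leaves the scale problem in place.

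**Conclusion.** The point holds in a limited form. With a valid standard error, the interaction as specified has essentially no power for a non-donor-only effect (5.0% at the planned size, 5.4% for a five-fold rise) and low power for a moderate crossover (15% and 48%). The log-odds scale gives 43%, 95%, 65% and 85% in the same four cases. A significant additive interaction is compatible with equal risk ratios, so on its own it says nothing about relative responsiveness.

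The size rests on the planning rates, 1:1 allocation, no exclusions and a robust standard error. The mechanism is less sensitive to them: with 813 donor addresses against 39,317 and base rates this far apart, donors dominate the variance under any similar figures. The primary analyses are unaffected. The change is worth making because it is cheap and, by the Project status section, outcome data had not been extracted, so the scale could still be fixed blind to results.

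**What to change.** In exploratory analysis 2:

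1. Keep the OLS interaction and label it as the absolute-scale contrast (a difference in percentage points).
2. Prespecify beside it a ratio-scale interaction: logistic or log-link regression with message, donor status and their product, tested by likelihood ratio or with Firth penalisation because counts are small.
3. Report the risk ratio in each stratum with its 95% CI.
4. State which question each scale answers, and that the OLS interaction is not to be read as a difference in relative responsiveness.

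The cost is a few lines of SAP text and one extra model; nothing planned is removed. There are two downsides. The two exploratory interaction results may differ, which is why item 4 is needed. And the ratio-scale test is only a partial remedy: about 43% power at the planned non-donor effect, with about 14 expected events in the smallest planning cell before exclusions, so a non-significant result should be reported as inconclusive.
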